While preliminary work is not necessary for a Planning Grant application (R34), our team has pilot data and expertise that is directly relevant to this application.

Development, feasibility and efficacy of the Tobacco Status Project (TSP). During her postdoctoral fellowship, [name] led a mixed-methods study to determine how young adult smokers would like to use Facebook to help change smoking behavior. About a third (31%) of survey respondents reported they would want to quit smoking using Facebook, and interest was greater among those more motivated to quit, who had made a quit attempt in the past year, and had previously used the Internet for assistance with a quit attempt (all $p<0.01$). In qualitative interviews, social support and convenience were identified as strengths of a Facebook intervention, while privacy was the main concern.⁴

[name] is currently funded with a five-year K23 career development award from NIDA to develop and test the feasibility and efficacy of Tobacco Status Project, combining Facebook contacts tailored to participants' readiness to quit smoking with a 12-week cessation program consisting of 7 state-of-the-art group cognitive-behavioral sessions occurring over Facebook text chat. A feasibility trial enrolled 79 young adults who formed 7 Facebook groups. Follow-up rates were 84% and 72% at 6 and 12 months, respectively, and reported 7-day abstinence was 21% at 6 months (9% biochemically-verified) and 18% at 12 months (9% verified).^{6,7} From baseline to 12-months, there was a significant increase in the proportion prepared to quit (13% to 46%, $p<.001$), 35% reduced their cigarette consumption by 50% or greater, and 67% reported a 24-hr quit attempt. Engagement in the intervention was high, with 92% participation in the full 3 month intervention and 61% commented on at least one post, with more commenting among those randomized to receive a personal monetary incentive.¹⁰⁹ Participants reported reading most of the Facebook posts (mean usability rating=3.3/4) and interactions from counseling sessions (3/4), thinking about what they read (3/4) and would recommend the program to others (3.3/4). Given low participation in CBT sessions (7 of 79 participated) but extremely high engagement (6/7 sessions attended on average) we incorporated the sessions directly into the Facebook groups for a larger efficacy trial currently underway.

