Final content for The [name] In sessions will be informed by the results of the focus groups and generated by [name] and [name] with collaboration from [name]. The [name] In sessions will be delivered by [name], who has also published in the area of alcohol use among young adults,^{154, 155} and a fellow in the UCSF Clinical Psychology Training Program who will both be supervised by [name]. With approximately 16 groups total (8 in each study condition, 4 Ready, 4 Not Ready, 10 members each on average), each therapist will conduct The [name] In sessions in 8 groups (2 Ready/2 Not Ready in each study condition).

Monetary Incentive for Engagement. Analyses of our TSP feasibility trial showed that a monetary incentive increased engagement in the Facebook intervention for all those who had some basic level of engagement (at least one Facebook comment).¹⁰⁹ In the RCT currently underway, groups are randomized to three different monetary incentive structures (daily, weekly, monthly) or no incentive. Although results are not final, preliminary analyses with 310 participants in the TSP condition in 10 TSP groups complete through 6/5/2015 (3 daily, 3 weekly, 1 monthly, 3 no incentive) indicate that any incentive is associated with higher engagement than no incentive (75% vs. 67% commenting at least once) and engagement is highest among those receiving an incentive in a weekly basis (82%). Thus in the present study, we will tally posts weekly and offer all participants a \$20 giftcard at the end of the intervention if they comment on all Facebook posts during the time period.

Nicotine Replacement Therapy (NRT).

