Sample size and power analysis. The sample N of 160 was set primarily for practical and clinical reasons and not driven by estimated effect sizes or hypothesis testing. We expect to have representation (although not equal) among males and females, and across ethnic groups consistent with our current trial of TSP. We also expect to have representation across levels of smoking and drinking, and readiness to quit using both substances. We anticipate an attrition rate of 30% at 3, 6, and 12 months, yielding a final sample size of 112 (56 in each group), enabling us to compare groups on primary and secondary outcomes at each timepoint. This will also generate an effect size estimate that will be useful for powering a larger trial.

A goal of 6 participants will be recruited per week during the 6-month recruitment period, which is in line with recruitment for our feasibility trial and current RCT.¹¹¹

Procedures. Participants will be recruited through Facebook and Craigslist advertisements, using a similar strategy to that of focus group and usability-testing. All advertisements will provide a link to the study’s website, with eligibility questions. If respondents are eligible, then they will be taken to the informed consent webpage. Participants consenting to participate in the study will be asked to verify age by sending proof through email or social media, a process used successfully in [name] previous research. Verified participants will be emailed a baseline assessment. Those completing the baseline assessment will be randomized to either TSP, or TSP+ALC, stratified based on readiness to quit smoking (Ready in the next 30 days, Not Ready in 30 days) and smoking pattern (daily vs. non-daily), variables known to be related to outcomes and addressed by the intervention.¹⁶¹ A stratified random assignment program will be developed in consultation with [name], and used currently in [name] RCT of TSP. All participants will then be assigned to a secret group tailored to their condition and readiness to quit tobacco. Groups will begin when there are approximately 12 participants enrolled, as that has been deemed the optimal number based on analyses of engagement in our previous work.^{109, 162} Groups will receive one social media post daily for 90 days and weekly “The [name] In” counseling sessions managed

[figure not shown]

Figure 2. Participant flow through the study

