- **Other health risk behaviors.** The 34-item *Staging Health Risk Assessment (S-HRA)*^{193, 194} will screen and assesses readiness to change for 11 health risk behaviors including tobacco, alcohol, and illicit drug use, poor sleep quality, sedentary behavior, poor diet, depression, and high risk sexual behavior. The staging algorithms for the health behaviors have been well studied and have strong predictive validity over 6, 12, 18, and 24 months.^{185, 186, 195-198} This measure will be used to characterize other health risk behaviors in this substance using sample with potential to evaluate the effect of each intervention on multiple health risk behaviors other than tobacco use and HED.
- **Feasibility Measures.** *Advertising statistics* available online through Facebook and participant characteristics will be used to track costs and recruitment over time at each study stage (e.g., study interest, meeting criteria, signing consent, and entering the study). *Retention* will be evaluated by the proportion of participants that completes the 3, 6, and 12-month assessments. *Engagement* will be measured by the total number of “likes” and comments each post/counseling session receives.
- **Usability measure.** A *usability measure*, adapted from our previous research,^{6, 7} will assess ease, comprehension, helpfulness, and likability of TSP and TSP+ALC interventions at 3 months.

C.9 Data Analysis.

Analysis for Specific Aim 2: Feasibility. Although we do not expect problems in implementing this intervention given our prior work with social media,⁷ we are evaluating feasibility outcomes to ensure feasibility of the TSP+ALC intervention.

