Analyses for Specific Aim 3 (Engagement and Patterns of Social Interaction). Analyses will use Facebook data extracted from the private groups we develop on Facebook using the Facebook API. All data will be de-identified and transferred to **[name]**, expert on social media analytics at Drexel University, for analysis. The data will include the content of the posts and comments, the activity of each participant (e.g., number, content, and time of all comments), and interactions among participants. We will determine patterns of engagement, type of posts that are most “engaging” to participants, and relate engagement to smoking and drinking outcomes using three main analyses: **(1) Patterns of engagement:** Total number of “likes” and comments to Facebook groups over the 3 month intervention period will be tallied for each group (TSP, TSP+ALC), and the non-parametric Kruskal-Wallis ANOVA will compare likes and comments in each intervention and include covariates of baseline characteristics (readiness to quit tobacco/alcohol, daily/non-daily smoking status, gender) and group membership; a social network analysis will examine the interaction patterns among different types of users with which participants engage in each intervention; a content analysis will evaluate the content of comments within each group and observe differences among the two groups; **(2) Success of specific posts:** To evaluate which posts are most successful at engaging participants, Drs. [name] and [name] will collaborate on coding posts based on content type (e.g., alcohol/tobacco, Motivational Interviewing, specific CBT skills). Specific codes will be determined upon design of the TSP+ALC intervention). ANOVA will then be used to examine likes and comments by post type within each group (TSP, TSP+ALC) **(3) Engagement and outcomes:** We will compare TSP and TSP+ALC groups on the relationship between intervention engagement (FB comments) and primary tobacco and alcohol outcomes (abstinence, heavy drinking days) at the end of the 3 month intervention period. Logistic regression will be used to analyze tobacco abstinence, and linear regression for days of heavy drinking at 3 months, controlling for any baseline differences in treatment groups. Kruskal-Wallis tests will evaluate the effect of incentive condition (personal, altruistic, no incentive) on comments to the Facebook group, in both the full sample and only those who made at least one comment to the group to address likely skewed data.

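### Aim 3 plans an incentive test for a factor this trial does not have, and a Kruskal-Wallis arm comparison that cannot carry its promised covariates and has no stated unit of analysis

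*Combined protocol and SAP*

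**What the plan says.** **Arm comparison.** In C.9 (Analyses for Specific Aim 3, first analysis), likes and comments over the three-month intervention are totalled for TSP and for TSP+ALC. Then "the non-parametric Kruskal-Wallis ANOVA will compare likes and comments in each intervention and include covariates of baseline characteristics". The listed covariates are readiness to quit tobacco and alcohol, daily or non-daily smoking, and gender; group membership is added to them. C.8 (Feasibility Measures) defines engagement differently, as the likes and "comments each post/counseling session receives". The Facebook extract described in C.9 also holds "the activity of each participant (e.g., number, content, and time of all comments".

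**Incentive test.** The Aim 3 text ends: "Kruskal-Wallis tests will evaluate the effect of incentive condition (personal, altruistic, no incentive) on comments to the Facebook group", to be run in everyone and again in those with at least one comment.

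**Design.** C.5 (Monetary Incentive for Engagement) says that "in the present study, we will tally posts weekly and offer all participants a" gift card, under one rule. C.8 (Procedures) says: "Those completing the baseline assessment will be randomized to either TSP, or TSP+ALC", with strata for readiness to quit smoking and smoking pattern. Each participant then joins a secret Facebook group specific to condition and tobacco readiness. C.5 expects "approximately 16 groups total (8 in each study condition, 4 Ready, 4 Not Ready, 10 members each on average".

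**The concern.** A plan should name an analysis that can be carried out on the data the trial will produce. Here one Aim 3 test has no factor to test. Another, the first analysis listed for that aim, promises an adjustment its method cannot make. Whoever does the work will have to choose the unit, the method and the handling of Facebook groups without guidance from the plan, possibly after seeing the engagement data. The choice matters because members of a Facebook group see and answer each other's comments. A test that treats participants as independent could take a few lively groups for an effect of arm.

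**Working it through.** The documents give no sample size, power or effect size for the Aim 3 tests, so there is no stated figure to reproduce.

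**1. Incentive test.** For k conditions, Kruskal-Wallis has k − 1 degrees of freedom. The plan names k = 3 (personal, altruistic, none), so df = 2. In this trial everyone has the same offer, so k = 1, df = 0 and no statistic exists. Incentives did vary in other trials: the feasibility trial randomised a personal incentive, and the TSP trial then under way used daily, weekly, monthly or none (C.5). An altruistic condition is mentioned nowhere outside the Aim 3 text.

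**2. Covariates.** Before tie correction, H = 12/(N(N+1)) × Σ(R_i²/n_i) − 3(N+1), where R_i is the rank sum and n_i the size of group i. Only pooled ranks and one grouping variable enter. With two arms, df = 1 and the test is equivalent to the Wilcoxon rank-sum test. There is no place for a covariate.

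**3. Unit.** Three units are in play: one total per arm (C.9), counts per post or session (C.8), and participants, to whom the covariates belong. Taken literally, arm totals give two numbers and no test.

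**4. Group membership.** If this means arm, it is the factor itself. If it means the Facebook group, each group lies within one arm and one readiness level. With 16 groups of 10 (16 × 10 = 160), a design matrix of 16 group indicators, arm and readiness has 18 columns and rank 16. The arm effect cannot then be estimated with groups as fixed effects.

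**5. Conditional illustration.** Suppose the analyst ran an unadjusted Kruskal-Wallis test on participants.
- From the documents: 8 groups of 10 per arm, and the share commenting at least once. That share was 61% in the feasibility trial ("61% commented on at least one post"), 73% in completed groups of the trial under way, and 82% under its weekly incentive.
- Assumed: gamma-Poisson counts with the shape solved to match those shares, mean comments of 15 or 5, and a between-group SD on the log scale of 0.3 or 0.5. There is no arm effect. Each cell has 10,000 simulated trials.

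Type I error at nominal 5%, for 61 / 73 / 82% commenting:

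| Mean comments | SD 0.3 | SD 0.5 |
|---|---|---|
| 15 | 5.6 / 6.9 / 8.0% | 7.6 / 10.3 / 12.6% |
| 5 | 6.6 / 8.1 / 10.2% | 9.7 / 14.1 / 19.2% |

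If half the between-group variance is due to readiness, which is balanced across arms, the range at mean 15 is 5.6% to 8.3% over both SDs. If groups do not differ, it is 4.7% to 5.5%. With the group as the unit, Kruskal-Wallis on 16 group totals gives 4.4% to 5.3%.

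**6. Candidate replacements.** Group mean ranks, with arm and readiness fitted, leave 16 − 3 = 13 df and rejected in 4.5% to 5.5% of trials in every 8-group cell. The next check had 1,500 trials per cell, 73% commenting, and adjustment for tobacco readiness, daily smoking and gender (Monte Carlo SE about 0.5 to 0.8 points):

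| Method | Mean 15, SD 0.3 | Mean 15, SD 0.5 | Mean 5, SD 0.5 |
|---|---|---|---|
| Covariate-adjusted group mean ranks | 5.6% | 4.9% | 5.9% |
| Negative binomial mixed model, Wald z | 7.2% | 10.3% | 10.7% |
| Same model, t on 13 df | 4.4% | 7.7% | 7.6% |

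Alcohol readiness, also a listed covariate, was not simulated.

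**The case against.** The strongest defence concerns the arm comparison. The plan does mention covariates and group membership, so its authors evidently meant to account for both, and a rank-based analysis of covariance is a plausible intent. Naming one would cure the covariate point. That is fair: this part is a method left unspecified, unlike the incentive test, which is impossible. It does not settle the unit or the meaning of group membership, and the Facebook group cannot simply be entered as a fixed covariate.

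A reader might infer from the simulated rates that the planned analysis has an inflated error rate. The documents do not support that. The rates belong to a fallback that drops both adjustments the plan promises, and they rest on a mean and an SD the documents do not give.

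A reader might also infer that the primary abstinence result is at risk. These two defects sit in the engagement tests and do not bear on it.

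On incentives, one could suppose that another trial's data were intended. The Aim 3 text draws its data from the private groups set up for the research and points to no other trial's data. The wording may have been carried over from earlier work, but that is conjecture.

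Finally, this is a pilot whose size was not set by hypothesis testing (C.8). That limits the weight of the point; it does not make either test feasible.

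**Conclusion.** Both defects stand on the text alone, whatever the simulation shows. The incentive test contradicts C.5 and C.8 and cannot be run. The arm comparison names a method that cannot deliver its stated adjustment, leaves the unit open, and uses a term for group membership that fails as a covariate under either reading. The numerical consequence is conditional: roughly 5.6% to 13% at an assumed mean of 15, up to about 20% at a mean of 5, and nominal if groups are alike, and then only for an unadjusted participant-level test. The plan should be corrected on this point. The effect is confined to the Aim 3 engagement results.

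**What to change.** **Incentive test.** Delete it, with its subset of participants who commented at least once, or reconcile C.5 and C.9 by stating which data supply the three conditions.

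**Arm comparison.**
- Make comments per participant the outcome; C.9 already lists these data.
- Replace Kruskal-Wallis with a covariate-adjusted rank analysis: rank the comments, regress the ranks on the listed baseline covariates without arm, and average the residuals within each Facebook group.
- Compare arms by a t-test on the roughly 16 group means, with about 13 df because tobacco readiness is a group-level covariate.
- Say what group membership means.
- If a rate ratio is wanted, add a negative binomial mixed model with a random Facebook-group intercept and label it descriptive, since even with t on 13 df it can reject above 5%.
- If likes are available only per post, account for both Facebook group and post.

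**Cost.** SAP wording, slightly more analysis, and no new data for comments. Nominal power is lower than for the invalid participant-level test: in simulation (mean 15, 73% commenting, SD 0.3 to 0.5) about 14–16% versus 21–24% at a rate ratio of 1.5, and 31–37% versus 46–47% at 2.0. Part of the gap reflects the participant-level test's inflated error rate. Report the estimate with its interval rather than relying on the p-value.

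The change is best made before any Phase II engagement data are examined; the documents do not show whether that stage has passed.

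### The covariate-adjusted Kruskal-Wallis comparison of likes and comments (Aim 3) cannot be run as written, and its group-membership covariate, if entered as a fixed Facebook-group term, removes the arm effect

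*Combined protocol and SAP*

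**What the plan says.** Section C.9, Analyses for Specific Aim 3, analysis (1), says that "the non-parametric Kruskal-Wallis ANOVA will compare likes and comments in each intervention" and that it will "include covariates of baseline characteristics (readiness to quit tobacco/alcohol, daily/non-daily smoking status, gender) and group membership". It does not say whether group membership is a fixed covariate, a random effect or a clustering term. Nor does it say whether the term means the Facebook group or the treatment arm. Earlier in the same sentence the totals "will be tallied for each group (TSP, TSP+ALC"), so there the word group denotes the arm.

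Two other sections fix the structure of the Facebook groups. Section C.8, Procedures, randomizes individuals ("Those completing the baseline assessment will be randomized to either TSP, or TSP+ALC") and then states: "All participants will then be assigned to a secret group tailored to their condition and readiness to quit tobacco". Section C.5, under TSP+ALC, gives the numbers: "With approximately 16 groups total (8 in each study condition, 4 Ready, 4 Not Ready, 10 members each on average").

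**The concern.** A covariate is useful in an arm comparison only if the arms overlap within its levels. Here they do not: once a participant's Facebook group is known, the arm is known, and so is the Ready/Not Ready level. An analyst who replaces Kruskal-Wallis with a regression and follows the written covariate list would be asking for an arm effect within Facebook groups, where arm never varies.

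The obvious escape, dropping the group term, has its own cost. Members of a Facebook group see the same posts and reply to one another, so their counts of likes and comments may well be correlated. Treating 160 participants as independent would then overstate the evidence for an arm difference. What is at stake is the planned between-arm test of likes and comments, under a Specific Aim devoted to engagement.

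**Working it through.** **Inputs.** From C.5: about 16 groups, 8 per arm, 4 Ready and 4 Not Ready in each arm, 10 members on average. From C.8: N = 160, individual randomization, groups specific to condition and tobacco readiness. From C.9: the covariate list. Assumed, because the documents give no figure: intraclass correlation (ICC) of engagement within a Facebook group of 0, 0.05, 0.10 or 0.20.

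**The plan's own figures.** 16 × 10 = 160 and 8 × 10 = 80 per arm, so the group structure and the sample size agree.

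**Step 1: the named test.** Kruskal-Wallis compares ranks across the levels of one factor and has no place for covariates. As named, it gives an unadjusted arm comparison. The model that would carry the covariates is not specified.

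**Step 2: Facebook group as a fixed covariate.** The columns are intercept, arm, binary tobacco readiness, daily smoking, gender and alcohol readiness (6), plus 16 − 1 = 15 group indicators: 21 columns.
- The rank is 19. Intercept and group indicators span 16 dimensions; daily smoking, gender and alcohol readiness add 3.
- Removing the arm column leaves the rank at 19. Arm adds nothing once group is in, and its residual sum of squares given group is 0.
- The second lost dimension is binary tobacco readiness, which is also constant within each group.
- Without the group indicators the matrix has full rank (6 of 6) and arm is estimable.

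This does not depend on the ICC. C.8 also says that groups start at about 12 participants; 160 / 12 gives about 13 groups, and the aliasing is the same.

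**Step 3: group membership read as the arm.** The term duplicates the factor under test. Arm is estimated once and nothing absorbs it, but no allowance is made for Facebook groups. With m = 10 members, the variance of the arm difference is inflated by the design effect 1 + (m − 1) × ICC. A test that ignores this, nominally at 5%, rejects under no arm effect with probability of approximately 2 × [1 − Φ(1.96 / √design effect)].

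| Assumed ICC | Design effect | 1.96 / √design effect | Approximate type I error | Simulated, plain Kruskal-Wallis |
|---|---|---|---|---|
| 0 | 1.00 | 1.960 | 5.0% | 5.2% |
| 0.05 | 1.45 | 1.628 | 10.4% | 10.9% |
| 0.10 | 1.90 | 1.422 | 15.5% | 15.7% |
| 0.20 | 2.80 | 1.171 | 24.1% | 24.0% |

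The simulations used normal outcomes. The formula and the simulation agree closely.

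**Step 4: Facebook group as a random intercept.** Arm is estimable. In standard deviation units its standard error is √[(4 / 160) × design effect]: 0.158, 0.190, 0.218 and 0.265 at ICC 0, 0.05, 0.10 and 0.20. Between-group degrees of freedom are 16 − 3 = 13 after intercept, arm and readiness.

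**The case against.** The plan never says that group membership is a fixed effect. A random intercept uses group membership, accepts the other covariates and estimates the arm effect. A reader might infer from the nesting that the engagement difference cannot be estimated in any model that takes covariates; that is wrong, and the documents do not support it. The loss of the arm effect is conditional on a fixed Facebook-group term. The fixed reading is nevertheless the natural one: the term is listed beside gender and smoking status, and the primary and secondary outcome analyses in C.9 name mixed-effects models where they are intended, whereas Aim 3 names none.

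The arm reading is also live, given how the same sentence uses the word. Someone might infer that it too destroys the comparison. It does not; it only repeats a term. What it leaves is the unaddressed clustering.

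Nor is all readiness information lost. Groups are formed on the binary tobacco split only. Alcohol readiness does not determine the Facebook group, and tobacco readiness is measured in five stages in C.8, Measures, so variation within a Not Ready group can remain.

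Finally, this is one engagement comparison in a pilot, and C.8 says: "The sample N of 160 was set primarily for practical and clinical reasons and not driven by estimated effect sizes or hypothesis testing". Aliasing would also probably be noticed when the model is fitted. Both points limit the consequence. They do not tell the analyst what to fit instead, and a choice made after seeing the data is what the plan should prevent.

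**Conclusion.** The point holds in conditional form. None of the three readings considered gives a sound adjusted comparison: Kruskal-Wallis cannot take the covariates; a fixed Facebook-group term fully aliases arm and binary tobacco readiness; and reading the term as the arm leaves clustering unaddressed. The aliasing is exact and needs only the nesting stated in C.5 and C.8. The type I error of about 11% to 24% rests on an assumed ICC of 0.05 to 0.20, 10 members per group and normal outcomes; at an ICC of zero there is no inflation.

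The scope is Aim 3 analysis (1) only. A reader might extend the point to the smoking result, but the primary abstinence model in C.9 does not list group membership, so this aliasing does not touch it. The plan should be corrected before analysis; the trial's design is not in question.

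**What to change.** In C.9, Aim 3 analysis (1):
- Define group membership as the Facebook group and remove it from the fixed covariates.
- Replace the covariate-adjusted Kruskal-Wallis test with a count model for each participant's likes and comments. Fixed effects: arm, readiness, smoking pattern and gender. Random intercept: Facebook group, nested within arm and readiness.
- Alternatively, compare group-level means between the arms (8 against 8), adjusting for readiness.

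This rewrites one sentence and needs no new data. The cost is precision: the arm test rests on about 16 groups, about 13 degrees of freedom, and its interval is wider than one that ignores groups. At an assumed ICC of 0.10, for example, the standard error is 0.218 rather than 0.158 standard deviations. If groups fill to about 12, there are about 13 groups and the degrees of freedom fall to about 13 − 3 = 10.
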